### **Surgical Site Occurrence**

A surgical site occurrence (SSO) will be defined as a complication or adverse event occurring at the surgical site, including but not limited to, superficial, deep incisional, and organ/space surgical site infections. Consensus definitions and treatment plans for common SSOs following open complex ventral hernia repair were developed *a priori* by the co-investigators for the purposes of this study protocol (Appendix 6). All study co-investigators agree to follow these consensus definitions and treatment plans for study subjects enrolled in this trial to maximize objectivity of this outcome measure.

## **Surgical Site Occurrences Requiring Procedural Intervention**

A surgical site occurrence requiring procedural intervention (SSOPI) will be defined as a complication or adverse event occurring at a surgical site that is managed or treated with an invasive procedure. Consensus definitions and treatment plans for common SSOs following open complex ventral hernia repair were developed *a priori* by the co-investigators for the purposes of this study protocol (Appendix 6). All study co-investigators agree to follow these consensus definitions and treatment plans for study subjects enrolled in this trial to maximize objectivity of this study measure.

## **Ventral Hernia Recurrence**

A ventral hernia recurrence (HR) will be defined as any fascial defect of the anterior abdominal wall located within 7 cm of the index ventral hernia repair site detected by physical exam or abdominal computed tomography (CT) examination. These defects will be categorized as to whether they occur at the midline or parastomal hernia site, or both. Alternatively, for patients that are not amenable to come to the hospital for an in-person visit, recurrence will be assessed using a validated patient-reported outcome tool denominated the Ventral Hernia Recurrence Inventory (VHRI).[32] The VHRI is a short 3-question survey that can be applied in person or through a telephone contact, and was shown to have higher sensitivity and specificity to diagnose hernia recurrence than physical examination. Also, it was shown to have the ability to rule out

hernia recurrence when patients answer “no” to its questions. All study co-investigators agree to follow this consensus definition of ventral hernia recurrence for study subjects enrolled in this trial to maximize objectivity of this study measure.

### **RISKS AND DISCOMFORTS**

As with any surgical procedure, there are some risks that are associated and they will be discussed in a separate surgical consent form. The subjects may experience some pain, bleeding and discomfort; however this is with any surgical operation. Common occurrences following hernia repair include seroma or hematoma around the hernia repair, inflammation, opening of the wound, or infection. Subjects may also experience additional therapies or treatments, including the removal of the mesh to treat any of these events.

### **BENEFITS**

There are no direct benefits to subjects for participating in this study. Subject participation will help us better understand the comparative safety and effectiveness of synthetic versus biologic meshes in clean-contaminated and contaminated open ventral hernia repair.

### **COSTS TO THE SUBJECTS**

27

Version date 4/17/19

CCF #7

NCT02451176

There are no extra costs to the subjects associated with the research.

Procedures related to the hernia surgery are considered standard of care and will be the responsibility of the subject and the subject's insurance company.

### **ALTERNATIVES TO PARTICIPATION**

The subjects are under no obligation to participate in this study. The subjects may decide not to have mesh used for their hernia repairs. The PI or surgeon co-investigator at each site will discuss all available options. Those subjects not willing to participate in this study may be considered for the alternative treatment of primary defect closure/hernia repair with or without a similar biologic or synthetic product.

### **PAYMENTS TO THE SUBJECTS**

Patients will not be paid for participation in this study.

### **PLAN FOR OBTAINING INFORMED CONSENT**

For each subject, written informed consent will be obtained prior to any protocol-related activities. As part of this procedure, the principal investigator, surgeon co-investigator, or one of the approved study coordinators must explain orally and in writing the nature, duration, and purpose of the study in such a manner that the subject is aware of the potential risks, inconveniences, or adverse effects that may occur. The subjects will be informed that they may withdraw from the study at any time. Subjects will receive all information that is required by federal regulations.

After a potential study patient is identified, the investigator or the study coordinator listed in this protocol as a person who will obtain consent will be responsible for instituting the informed consent process in a face-to-face manner. Before starting any study procedures, the investigator will discuss the proposed research study in detail with the potential subject during the office visit to discuss treatment options. The subject will be allowed ample time to read and review the informed consent document, and ask questions. The informed consent document will be reviewed with the subject in depth by the participating investigator or designated member of the research team to ensure that the potential participant has a good understanding of the study protocol; what is required of the study participants; the potential risks and benefits of study participation; and his or her rights as a study participant. The investigators will be available by phone or office visit to answer any questions that the participant may have. After consideration, the subject may return if necessary for another visit with the investigator to discuss the study, ask questions, and sign the informed consent document to participate in this study.

After the subject has read and reviewed the informed consent document and has agreed to participate, he/she will be asked to sign and date the document. The study member obtaining consent will also sign and date the form, and documentation of the informed consent process will be included in the research file (i.e., the person who obtained consent, where and when consent was

obtained, and who was present during the process). A copy of the consent form will be given to the subject.

### **PROVISIONS FOR SUBJECTS FROM VULNERABLE POPULATIONS**

The population to be studied includes adults 21 years of age or over, so children are therefore excluded. Decisionally-impaired and cognitively-impaired persons will not be approached to participate in this study as we are seeking subjects who have the capacity to understand and actively consent to the procedure independently. Pregnant women will be excluded from participating in this study.

Staff and employees of the participating sites (Cleveland Clinic, Greenville Health Systems Vanderbilt University Medical Center, and Washington University ) are considered vulnerable populations. Staff and employees of any of the participating sites may be eligible to participate in this study. Since subjects may or may not benefit from this study, we do not want to exclude this population. If an employee is a potential candidate for this study, the subject will be informed during the consent process that his/her participation or refusal to will in no way influence grades, employment, or subsequent recommendations. Every effort will be made to prevent coercion during this initial process and throughout study participation. According to IRB policy, students and house staff cannot be asked to participate in research conducted while under the direct supervision of the investigator, so those subjects will not be enrolled.

In those instances where potential participants cannot read the consent form because they do not speak English, we will work with the IRB to develop a language-appropriate consent form. In addition, a qualified translator will be present to assist with obtaining the informed consent of the participant.

In addition, in the unusual situation where a subject cannot read a consent form due to illiteracy or blindness, a member of the research study staff will read and explain the consent form to the participant or to the participant's legally-authorized representative. A witness, who will sign and date the consent form, must also be present during this oral presentation.

### **SUBJECT PRIVACY AND DATA CONFIDENTIALITY**

Anonymity and confidentiality of subjects participating in this study will be maintained. The only potential identifiers on any study documents submitted to the sponsor or designee will be subject study numbers, dates of birth, and dates of procedures. Every effort will be made to maintain the confidentiality of documents that identify the subject by name (e.g., signed informed consent documents, clinic charts), except to the extent necessary to allow monitoring by the Center for Clinical Research at Cleveland Clinic, internal monitoring by any of the participating sites, or auditing by the FDA or other regulatory authorities. Should the name and/or address of a subject participating in this trial be on a document submitted to the FDA or other regulatory authority (e.g., laboratory

report), the name and/or address will be completely blocked out and replaced with the subject study number.

Additionally, patient charts and clinical records will be requested and reviewed so that protocol adherence and source documentation can be verified. There is a possibility that the Institutional Review Boards of any of the participating sites, the Food and Drug Administration, and possibly foreign regulatory agencies may review the de-identified study records.

All information collected, such as name or medical record number, will be stored utilizing a customized Research Electronic Data Capture (REDCap®) database program for multi-institutional data collection. This is in a secure network/firewall protected electronic database to which only the investigator and the designated members of the study team will have access using an individual assigned login and password. Only approved study members listed on the IRB protocol will have access to the separately-stored master list. User rights will be assigned such that the designated research coordinator at each site may only enter and review data from that site. Only the Principal Investigator, Lead Research Coordinators, and Biostatisticians will be granted access to retrieve patient data from all sites for routine data quality assessments and data analyses. All electronic records pertaining to the clinical study will be password-protected, and only approved study members listed on the IRB protocol will have password access.

Any information about the subject collected on paper, as well as the subject enrollment log linking the subjects to their identifiers, will be kept under lock and key in the Department of Surgery at the corresponding participating site.

### *Anticipated results and limitations*

We expect that the synthetic mesh may be associated with an initial higher rate of mesh infections than a biologic mesh. However, we also believe that these infections will be treatable with local measures and not require surgical excision of the mesh. We believe that light-weight macroporous materials will granulate and heal without long-term adverse outcomes. This should result in a significant reduction in long-term hernia recurrences with the synthetic material. Another concern with this trial is the ability to recruit enough patients meeting inclusion criteria. The multi-center nature of this study with well-established expert hernia surgeons with extensive experience in complex abdominal wall reconstruction should significantly reduce the risk of poor enrollment. Each program is a high-volume referral center for complex abdominal reconstructions performing on average of 4 cases per week. Finally, the ability to generalize our results to all available biologic mesh and synthetic mesh will not be possible. However, if the synthetic mesh is proven safe and effective in the single-stage repair of clean-contaminated and contaminated defects, it is likely that no surgeon will utilize any biologic graft costing over 100 times the price.

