### **Deep Incisional SSI**

A **deep incisional SSI** must meet the following criteria:

Infection occurs within 30 or 90 days after the operative procedure AND the infection involves deep soft tissues (e.g., fascial and muscle layers) of the incision AND patient has at least ONE of the following:

- a. purulent drainage from the deep incision but not from the organ/space component of the surgical site
- b. a deep incision spontaneously dehisces or is deliberately opened by a surgeon AND is culture-positive or not cultured AND the patient has at least one of the following signs or symptoms: fever ( $>38^{\circ}\text{C}$ ), or localized pain, or tenderness. A culture-negative finding does not meet this criterion.
- c. an abscess or other evidence of infection involving the deep incision is found on direct examination, during invasive procedure, or by histopathologic examination or imaging test.
- d. diagnosis of a deep incisional SSI by a surgeon or attending physician.

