### **Primary Analyses of Primary Outcomes:**

The primary outcomes are rates of surgical site occurrences requiring procedural intervention (SSOPI) and hernia recurrence (HR) assessed postoperatively at 1 month, 6 months, 12 months, and 24 months. For SSOPI with 4 repeated binary measurements, a generalized mixed model analysis with repeated measures will be performed to determine if a significant difference exists between the biologic mesh and the permanent synthetic mesh cohorts in the rate of SSOPI. For HR, which is a single binary outcome, simple chi-square tests will be used for unadjusted analyses and a logistic regression model will be used for adjusted analyses. As this is a randomized trial, differences in baseline demographic and clinical characteristics between the biologic mesh cohort and the permanent synthetic mesh cohort are expected to occur at random. Any significant differences found among the demographic or preoperative clinical characteristics between the two treatment groups will be controlled for in the final analysis to limit potential confounding of results.

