### **Analyses of Secondary Outcomes:**

The secondary outcomes are pain and quality of life (QOL). The assessment of the association between these outcomes and mesh type will parallel what was described above for the primary outcome. The differences are as follows. First, the primary analysis will utilize an ANCOVA model adjusting for baseline pain (QOL) and correlations among repeated measurements. The null hypothesis is that the pain (QOL) is the same, on average, between the synthetic and biologic mesh groups (H0: Beta-mesh-type = 0). The alternative hypothesis is that the pain (QOL) is different, on average, between the two groups (H1: Beta-mesh-type not= 0). Second, the multivariable modeling will utilize multiple linear regressions. A mixed model analysis with repeated measures will be performed to determine if a significant difference exists between the biologic mesh and the permanent synthetic mesh cohorts in the mean change in score from the preoperative assessment to the postoperative assessments at 1 month, 6 months, 12 months, and 24 months for the EQ-5D and HerQLes quality of life instruments. The null hypothesis is that there is no significant difference between the biologic mesh and the permanent synthetic mesh cohorts in the mean change in score from the preoperative to the postoperative assessments at any of the time points for either the EQ-5D or the HerQLes quality of life instruments. The alternate hypothesis is that there is a significantly greater change in EQ-5D

and HerQLes scores from the preoperative assessment to the postoperative assessment at each of the time points for the permanent synthetic mesh cohort compared to the biologic mesh cohort

In these data analyses, we will explore the possibility of medical center effect and treatment by medical center interaction. In particular, in the regression analyses, we will use indicator variables for medical center effect and indicator variable\*treatment for possible treatment by medical center interaction. If treatment by medical center interaction is significant, then it is more appropriate that the treatment effects are summarized by medical center.

**Specific Aim 2 - Demonstrate that a macroporous light-weight polypropylene mesh is the more cost-effective strategy than a biologic prosthetic in clean-contaminated and contaminated abdominal wall reconstruction.**

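### The plan expects more mesh infections with synthetic mesh but compares neither mesh infection nor mesh removal separately; both are seen only inside SSOPI, and only when a procedure is done

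*Combined protocol and SAP*

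**What the plan says.** The Specific Aims and Significance sections say the study compares the safety, as well as the efficacy and cost-effectiveness, of the two materials. 'Anticipated results and limitations' then makes three statements that bear on safety:

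- An arm-specific risk: "We expect that the synthetic mesh may be associated with an initial higher rate of mesh infections than a biologic mesh".
- A belief that makes the risk acceptable: "we also believe that these infections will be treatable with local measures and not require surgical excision of the mesh".
- A conclusion the trial might support: "if the synthetic mesh is proven safe and effective in the single-stage repair of clean-contaminated and contaminated defects", after which surgeons are expected to abandon the costlier biologic grafts.

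The Aim 1 analyses are these:

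- 'Primary Analyses of Primary Outcomes': "The primary outcomes are rates of surgical site occurrences requiring procedural intervention (SSOPI) and hernia recurrence (HR".
- 'Secondary Analyses of Primary Outcomes': time to a healed wound and time to recurrence.
- 'Analyses of Secondary Outcomes': "The secondary outcomes are pain and quality of life (QOL".

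SSOPI is defined as "a complication or adverse event occurring at a surgical site that is managed or treated with an invasive procedure". The wider class, surgical site occurrence (SSO), includes all three surgical site infection (SSI) types. 'Risks and Discomforts' lists mesh removal among the possible treatments of wound events. SSIs, SSOs, procedures for SSOs and reoperations are recorded ('Study Procedures'), but no comparison of SSI between arms is specified. In the available text, an infected mesh is described only in an exclusion criterion about prior synthetic mesh.

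**The concern.** The plan makes two testable statements about the safety of the synthetic arm: more mesh infections, but no excisions. It collects most of the data needed to examine both, yet specifies no analysis that would show either one.

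SSOPI cannot do this alone, for two reasons. It omits infections managed without a procedure. It also gives a mesh removal the same weight as a minor wound procedure. The outcome that carries the safety comparison is expected to favour synthetic mesh strongly, while the named risk is expected to favour biologic mesh. A trial run exactly to plan could report a clear SSOPI benefit and leave readers unable to see whether mesh infections or removals were in excess. That matters because the Innovation section expects the results to set the standard of care.

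**Working it through.** **1. The plan's own figures.** The Power Calculation gives 101 evaluable patients per arm, hernia recurrence of 29.21% vs 9.01%, SSOPI of 39.02% vs 9.01%, and an overall two-sided alpha of 0.05 over two hypotheses. I take 0.025 for each, which is an assumption about the split. The formula is power = Φ{(d − z·s0)/s1}, with s0 = √[2p̄(1−p̄)/n], s1 = √[(p1(1−p1)+p2(1−p2))/n] and z = 2.2414.

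- Recurrence: d = 0.2020, s0 = 0.0553, s1 = 0.0535. The argument is 1.459 and power is 92.8% (stated: 92%).
- SSOPI as a single binary outcome: 99.8% (stated: 100%, for a four-measurement model that I did not rebuild).
- Enrolment: 202/0.8 = 252.5, rounded up to 253, as stated.

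The inputs are confirmed. The issue is the choice of outcomes, not a wrong number.

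**2. Where each event would be counted.**

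| Event | Planned comparison that captures it |
|---|---|
| Mesh infection, invasive procedure done | SSOPI, pooled with all other procedures |
| Mesh removal for a surgical-site complication | SSOPI, pooled, same weight as any other procedure |
| Mesh infection, no invasive procedure | None specific to infection; indirectly time to healed wound, pain, QOL or costs |

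The recorded SSI categories do not fill the gap. They are classed by tissue depth, not by mesh involvement. The superficial category ends at 30 days, and the deep and organ/space categories read "Infection occurs within 30 or 90 days after the operative procedure". Follow-up runs to 24 months.

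**3. Can an SSOPI win coexist with an excess of the named risk?** Suppose extra mesh-related procedures raise synthetic SSOPI above 9.01%, with biologic SSOPI staying at 39.02%. The increments are assumptions. Single binary outcome, alpha 0.025, 101 per arm:

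- +5 points (14.01%): d = 0.2501, s0 = 0.0621, s1 = 0.0596; power 96.9%.
- +10 points (19.01%): d = 0.2001, s0 = 0.0639, s1 = 0.0623; power 82.0%.

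So yes. About 10 extra synthetic patients in 101 with mesh-related procedures would still leave SSOPI likely to favour synthetic mesh.

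**4. Loss of severity (illustration only).** At the planned rates SSOPI is about 39 vs 9 patients. The pooled test gives z = 0.2970/0.0599 = 4.96, whatever the 9 synthetic procedures were. At the extreme, where all 9 were removals against none in the biologic arm, a direct comparison gives z = 0.0891/0.0290 = 3.07, p = 0.002, in the opposite direction. Nothing in the documents suggests that this extreme is likely. It shows only that SSOPI cannot tell the cases apart.

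**5. What separate reporting would deliver.** The documents give no rate of mesh infection or removal. As an assumed range I use 8% to 15%, the general SSI rates that the Significance section gives for clean-contaminated and contaminated fields. The 95% half-width is 1.96·√[(p1(1−p1)+p2(1−p2))/101]:

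- 8% vs 8%: 7.5 points
- 15% vs 8%: 8.7 points
- 15% vs 15%: 9.8 points

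For removal, 0/101 gives an exact two-sided 95% upper limit of 1 − 0.025^(1/101) = 3.6%.

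As a test, at two-sided alpha 0.05, power would be 38% for 1% vs 5%, 27% for 5% vs 10%, and 81% only for a gap as wide as 1% vs 10%.

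**The case against.** A reader might infer that mesh infection and mesh removal lie outside every planned comparison, so that the trial leaves its named risk untested. The documents do not support that. SSO covers all SSI types and is not limited to them, SSOPI is any such event handled invasively, and mesh removal is a listed treatment. Procedure-treated mesh infections and removals for surgical-site complications therefore enter a primary outcome. SSO and SSOPI carry no 30- or 90-day limit, and the Study Design section runs SSOPI to 24 months, so a late mesh infection needing a procedure counts. Time to a healed wound is also analysed, and Aim 2 includes the costs of complications.

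Four further objections have force:

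- Local measures are contrasted only with excision, so they may include opening or draining a wound. How much infection escapes SSOPI is unknown.
- Appendix 6, which holds the SSO definitions and treatment plans, appears by title only. It may define mesh infection, so no claim can be made that a definition is missing.
- The remark about synthetic mesh being proven safe is a conditional comment on surgeon uptake, not a decision rule.
- A separate comparison would have low power.

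All of this narrows the point without removing it. Pooling still hides direction and severity, and infections managed without a procedure still have no comparison of their own. Low power argues against a formal test, not against an interval estimate.

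**Conclusion.** The point holds in this form: there is no separate between-arm comparison of mesh infection or mesh removal. Both are visible only within SSOPI when a procedure is done, mixed with all other wound procedures. An SSOPI result favouring synthetic mesh could therefore coexist with an excess of the one risk the plan assigns to that arm. Power for an SSOPI win stays at about 97% or 82% if the synthetic rate rises by an assumed 5 or 10 points.

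This rests on the planned SSOPI rates, 101 evaluable patients per arm, an equal split of alpha, and SSOPI treated as one binary outcome. It does not show that an excess is likely, nor that the primary analysis is invalid. It is a worthwhile, cheap improvement to the safety reporting and leaves the sample size and primary outcomes untouched.

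**What to change.** In 'Analyses of Secondary Outcomes', add two secondary safety outcomes. Report each by arm, from surgery to 24 months, as the proportion of patients affected with a risk difference and 95% CI:

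1. Infection involving the study mesh, however treated and without the 30- or 90-day SSI cut-off. Use one material-neutral definition applied identically in both arms, consistent with Appendix 6 if it has one. The exclusion-criterion wording should not be borrowed: it describes a prior synthetic mesh and could lead to different ascertainment in the biologic arm.
2. Partial or complete removal of the study mesh.

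Also tabulate SSOPI by type of procedure, with mesh removal as its own row, and base any safety conclusion on these results alongside SSOPI. Label both outcomes as estimation rather than powered tests.

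The cost is a few tables and possibly a small addition to the case report form, since SSIs, SSOs, procedures and reoperations are already recorded. Clinical care, sample size and the primary analysis do not change. The drawbacks are wide intervals and a safety message that may turn out less favourable to synthetic mesh.
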